3.2. Modified Full Analysis Set (mFAS)

The modified full analysis set (mFAS) includes all randomized subjects who have been vaccinated with at least one dose and have a negative serology test result from the central laboratory test at baseline; it is based on the treatment received (as treated).

3.3. Randomized Analysis Set

The randomized analysis set includes all randomized subjects; it is based on the treatment allocated by the IWRS (as randomized).

3.4. Safety Analysis Set (SAF)

The safety analysis set (SAF) includes all randomized subjects who have been vaccinated with at least one dose or received any study drug; it is based on the treatment received (as treated). Treatment compliance/administration and all clinical safety variables will be analyzed using the SAF.

3.5. Vaccine Booster Analysis Set

The vaccine booster analysis set includes Per Protocol Set subjects who signed the optional sub-study informed consent, have been vaccinated with the study-provided vaccine booster and did not have an adverse event of COVID (Preferred Terms of ‘COVID-19’, ‘Asymptomatic COVID-19’, ‘SARS-CoV-2 test positive’, ‘COVID-19 pneumonia’) or a positive PCR test prior to the post-booster follow-up sample collection.

3.6. The Pharmacokinetic Analysis Set

The pharmacokinetics (PK) analysis sets (PKAS) are defined for each study drug separately and includes all subjects who received any study drug and who had at least 1 non-missing result following the first dose of the respective study drug. Subjects will be analyzed based on actual treatment received.

3.7. Immunogenicity Analysis Sets

The ADA analysis sets (AAS) are defined for each study drug separately and include all subjects who received any study drug (safety analysis set) and had at least one non-missing ADA result following the first dose of the respective study drug. The ADA analysis sets are based on the actual treatment received (as treated) rather than as randomized.

The NAb analysis sets (NAbAS) are defined for each study drug separately and include all treated subjects that are included in the ADA analysis set and that tested negative at all ADA sampling times or tested positive at one or more post-dose ADA sampling times and had at least one non-missing post-dose NAb result (either imputed or analysis result). Samples that tested negative for ADA are not assayed in the NAb assay and the corresponding NAb results are imputed as negative and included as such in the NAb analysis set. Subjects in the NAbAS with multiple post-dose ADA results which consist of both imputed NAb-negative result(s) for ADA negative samples and only missing NAb results for all ADA-positive result(s), are set to NAb negative. Subjects in the NAbAS that have at least one post-dose positive NAb analysis result are set to NAb positive even if other NAb results are missing.

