11.3.5. Immunogenicity Analysis Sets

The ADA analysis sets include all subjects who received any study drug and had at least 1 non-missing ADA result from the ADA assays after first dose of study drug.

The NAb analysis sets include all subjects who received any study drug and who are either negative in the ADA assays or positive for ADA with at least one non-missing result in the NAb assays after first dose of the study drug. Subjects who are negative in the ADA assays are set to negative in the NAb analysis sets.

Subjects will be analyzed according to the treatment actually received.

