1.2.5. Modifications from the Statistical Section in the Final Protocol

Modifications in the Statistical Analysis Plan from the Statistical Section in the Final Protocol include the addition of Viral Neutralizing Titer and converted World Health Organization standard unit parameters as additional efficacy variables, further detailing of exclusion criteria for the Per Protocol Set and added exclusion details for the vaccine booster analysis set as subset of the Per Protocol Set.

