4.8. Immunogenicity Variables

The immunogenicity variables are ADA response status, titer, and NAb status at nominal sampling time/visit. Serum samples for immunogenicity analysis will be collected at the timepoints outlined in the Schedule of Events (Appendix 11.1). Samples positive in the ADA assays will be further characterized for ADA titers and for the presence of NAb.

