5.10.2. Analysis of NAb Data

The absolute occurrence (n) and percent of subjects (%) with NAb status in the NAb analysis sets will be provided by treatment groups. The NAb status is categorized as follows:

- Negative: Samples tested negative in the ADA assays, or samples positive in the ADA assays but tested negative in the NAb assays, or ADA-positive results without NAb analysis results.
- Positive: Samples tested positive in the NAb assays.

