5.10.3. Association of Immunogenicity with Exposure, Safety and Efficacy

5.10.3.1. Immunogenicity and Exposure

Potential association between immunogenicity and systemic exposure to REGN10933 and REGN10987 will be explored by treatment groups. Plots of individual REGN10933 and REGN10987 concentration time profiles may be provided to examine the potential impact of ADA category, maximum titer category and NAb status on these profiles.

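### SAP 3.7 counts an ADA-positive subject whose ADA-positive samples were never NAb-tested as NAb-negative, where Protocol 11.3.5 excludes that subject, and SAP 1.2.5 does not list the change (minor)

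*SAP*

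**What the plan says.** Protocol 11.3.5 lets two kinds of treated subject into the NAb analysis sets: those negative for ADA, who are set to NAb-negative, and those "positive for ADA with at least one non-missing result in the NAb assays after first dose of the study drug". Protocol 11.4.9 defines ADA-negative as negative at every time point, so one positive sample takes a subject out of the first group.

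SAP 3.7 also admits subjects negative throughout. For a subject with a positive post-dose ADA sample, it requires that the subject "had at least one non-missing post-dose NAb result (either imputed or analysis result"). ADA-negative samples are not run in the NAb assay; their NAb result is imputed as negative. For subjects with several post-dose ADA results that mix imputed negatives with untested positives, it adds that those having "only missing NAb results for all ADA-positive result(s), are set to NAb negative".

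SAP 5.10.2 says that the number and "percent of subjects (%) with NAb status in the NAb analysis sets will be provided by treatment groups". Its Negative category includes "samples positive in the ADA assays but tested negative in the NAb assays, or ADA-positive results without NAb analysis results".

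SAP 1.2.5, on modifications from the protocol, names the additional titer and unit variables, "further detailing of exclusion criteria for the Per Protocol Set and added exclusion details for the vaccine booster analysis set". It has no item on the NAb or ADA sets. SAP 1.2.6 logs edits to 3.7, 5.10.1 and 5.10.2 between SAP versions 1 and 2, and describes them as clarification.

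**The concern.** Imputing NAb-negative for an ADA-negative sample is not in dispute. The problem is letting that imputed value stand in for the subject's other samples. An ADA-negative sample at one visit says nothing about neutralization in an ADA-positive sample at another. For this subject the only informative sample was not tested, yet the table reports a negative finding.

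NAb to each antibody is part of a listed secondary endpoint, reported by arm as a count and percentage of the NAb set. Adding untested ADA-positive subjects to the denominator as negatives pushes the positive percentage one way only. NAb status may also label the individual concentration profiles in SAP 5.10.3.1, which are meant "to examine the potential impact of ADA category, maximum titer category and NAb status on these profiles"; there the subject would appear as NAb-negative.

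A second, smaller matter is that SAP 5.10.2 describes its categories in terms of samples while the table counts subjects. It also omits the condition in 3.7 that an ADA-negative sample must exist.

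**Working it through.** The documents give no figure for this point, so there is none to reproduce. The check has three steps.

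**Step 1. Which subjects are classified differently?** Take each post-dose ADA sample as N (ADA-negative) or as ADA-positive with NAb negative (P−), positive (P+) or missing (P?). All patterns of one or two samples were classified under both texts. These four show where the rules agree and differ:

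| Post-dose samples | Protocol 11.3.5 | SAP 3.7 |
|---|---|---|
| N, P+ | in, positive | in, positive |
| P−, P? | in, negative | in, negative |
| P?, P? (or P? alone) | out | out |
| **N, P?** | **out** | **in, negative** |

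Every other pattern agrees as well. N, P? is the only one that differs.

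**Step 2. How far can it move a percentage?** Let n be the subjects in the NAb set of an arm under the SAP rule, k the NAb-positive subjects and u the subjects of type N, P?.

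- SAP: k/n
- Protocol: k/(n − u)
- Difference: k·u / [n(n − u)], which is never negative

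n = 30 is the planned size of a study-drug arm (Protocol 11.2). The documents give no ADA rate or NAb failure rate, so k and u are assumed, each from 0 to 2.

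| k | u | SAP | Protocol | Difference (points) |
|---|---|---|---|---|
| 0 | any | 0% | 0% | 0 |
| 1 or 2 | 0 | 3.33% or 6.67% | same | 0 |
| 1 | 1 | 1/30 = 3.33% | 1/29 = 3.45% | 1/870 = 0.11 |
| 1 | 2 | 1/30 = 3.33% | 1/28 = 3.57% | 2/840 = 0.24 |
| 2 | 1 | 2/30 = 6.67% | 2/29 = 6.90% | 2/870 = 0.23 |
| 2 | 2 | 2/30 = 6.67% | 2/28 = 7.14% | 4/840 = 0.48 |

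When k = 0 both rules print 0%, but the SAP table does not show that u subjects were untested. Counting them as positive would give 1/30 = 3.3% for u = 1 or 2/30 = 6.7% for u = 2.

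**Step 3. Where can it arise?** The pattern needs two post-dose ADA results.

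- Control arms 6a to 6d give no ADA samples (Protocol 9.1.1, footnote 11).
- Protocol Tables 3 and 4 show a pre-dose ADA sample and two later ones, for arms 1, 2, 3, 7 and 8 and for arms 4 and 5.
- Protocol Table 5 shows, for arm 9, the pre-dose sample and one later sample. On schedule, arm 9 cannot produce the pattern.

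That leaves 7 arms × 30 = 210 planned subjects at most. This rests on the protocol tables as they read in the available text; table extraction may have lost or moved marks.

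**The case against.** The strongest reply is that almost nothing turns on this. SAP 4.8 states: "Samples positive in the ADA assays will be further characterized for ADA titers and for the presence of NAb". If that is carried out in full, u = 0 and the two rules agree. Even the largest illustrated difference, 0.48 points, is well under the 3.33 points that one subject in 30 carries. The exposure plots are optional, the NAb-positive group used in SAP 5.10.3.2 has the same members under both rules, no hypothesis is tested, and the primary endpoint is unaffected. All of this stands and is why the point is minor.

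It can also be said that the rule is written out openly in SAP 3.7, that Protocol section 11 presents itself as the basis for a SAP that may change, and that SAP 1.2.6 flags 3.7 as edited. This stands in part: the rule is visible and the edit is logged. But the log compares SAP versions and calls the edit a clarification. It does not tell the reader that the set now departs from the protocol, which is the purpose of SAP 1.2.5.

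The protocol rule is not perfect either. A subject with one NAb-negative and one untested ADA-positive sample enters as negative under both texts, and excluding untested subjects is itself an assumption about missing data. This is true, and it is the reason to report the number excluded.

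Two stronger readings are tempting. A reader might infer from SAP 5.10.2 that any ADA-positive subject without a NAb result counts as negative, contradicting 3.7. The documents do not support this: 5.10.2 tabulates only within the NAb sets, and 3.7 does not admit a subject whose post-dose samples are all ADA-positive and untested. The wording is ambiguous, not contradictory. A reader might also count all eight study-drug arms, 8 × 30 = 240 subjects, as exposed. The single scheduled post-dose ADA sample in arm 9 does not support that.

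**Conclusion.** The point holds as a minor one. For exactly one type of subject, SAP 3.7 and Protocol 11.3.5 give different results: the protocol excludes the subject and the SAP counts the subject as NAb-negative without a test of any ADA-positive sample. The departure is not declared in SAP 1.2.5. Its direction is fixed: the NAb-positive percentage falls or stays the same.

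The size is 0 to 0.48 percentage points, assuming 30 subjects in the arm's NAb set, at most two NAb-positive and at most two affected. It is zero if every ADA-positive sample is assayed or if the arm has no NAb-positive subject. The ceiling of seven arms and 210 planned subjects rests on the protocol's ADA schedule as it reads. Nothing here supports a claim that the NAb results would be materially misleading.

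**What to change.** - **SAP 3.7:** require an actual NAb assay result, not an imputed one, before an ADA-positive subject enters the NAb set, as Protocol 11.3.5 does. Remove the rule that sets the mixed, untested subject to negative.
- **SAP 5.10.2:** delete the last part of the Negative category, which takes in ADA-positive results that have no NAb analysis, and define both categories for subjects instead of samples.
- **Reporting:** give, by arm, the number of ADA-positive subjects excluded because they have no NAb assay result. A separate missing class inside the NAb set is not needed, since it would be empty once 3.7 is changed. An upper bound that counts the excluded subjects as positive is optional.

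If the sponsor prefers the SAP rule, the minimum is to list it in SAP 1.2.5 as a modification from the protocol and to repeat the condition of 3.7 in 5.10.2.

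The cost is one derivation rule, wording in two SAP sections and one count per arm, with no new data. The downside is a slightly smaller NAb denominator if any such subject exists.

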4. ANALYSIS VARIABLES

4.1. Demographics and Baseline Characteristics

Demographic and baseline characteristics will be obtained from the last available value up to the date of first dose of vaccine or REGN10933+REGN10987 (as applicable and whichever occurs first).

The following demographic variables will be tabulated:

- Age (years)
- Age categories (≥ 18 to < 45 , ≥ 45 to < 65 , ≥ 65 ; and < 65 , and ≥ 65 years)
- Sex (Male, Female)
- Race (American Indian/Alaskan Native, Asian, Black/African American, Native Hawaiian/Other Pacific Islander, White and Other)
- Ethnicity (Hispanic/Latino)
- Baseline Weight
- Baseline Height
- Baseline BMI
- Baseline SARS-CoV-2 RT-PCR result (local lab)
- Baseline SARS-CoV-2 serology results (central lab)

Additional baseline characteristics will be included if needed.

4.2. Medical History

Medical history will be coded to a Preferred Term (PT) and associated System Organ Class (SOC) according to Medical Dictionary for Regulatory Activities (MedDRA®).

4.3. Prior / Concomitant Medication & Procedures

Medications will be coded to an ATC Level 4, associated ATC Level 2, and standardized medication name according to the Anatomical Therapeutic Chemical Classification System. Procedures will be coded to a PT and associated SOC according to MedDRA®.

Prior medications/procedures are defined as those that were started/Performed prior to the first dose of vaccine or study drug (as applicable and whichever occurs first).

On-treatment medications/procedures are defined those taken (or continued to be taken)/performed following the first dose of vaccine or study drug (as applicable and whichever occurs first).

4.4. Prohibited Medication and Vaccine During Study

The use of the following concomitant medications and vaccines may not require withdrawal of the participant from the study but may determine a subject's evaluability in the analyses related to vaccine response (see Section 3.1).

- Investigational drugs
- Investigational or approved passive antibodies for SARS-CoV-2 infection prophylaxis (eg, convalescent plasma or sera, mAbs, hyperimmune globulin)
- Any other vaccine within 28 days prior to or after study drug administration, other than Moderna mRNA-1273 vaccine administered as part of this study

Exception: seasonal influenza vaccine is only prohibited within 14 days before or after study drug administration, or within 14 days before or after Moderna mRNA-1273 vaccine administration.

- Systemic medications that suppresses the immune system (for corticosteroids, ≥ 20 mg/day of prednisone equivalent), except for the treatment of COVID-19

4.5. Vaccine Response Variable

4.5.1. Primary Vaccine Response Variable

The primary endpoint is the 50% inhibitory dilution (ID50) neutralizing antibody titers of vaccine-induced neutralizing antibodies to SARS-CoV-2, assessed 56 days after the first dose of the vaccine (ie, the vaccine response assessment period). The 56-day time point corresponds to study day 71 for study arms 1, 2, 3, 7, 8, 6a, and 6c, and study day 57 for study arms 4, 5, 9, 6b, and 6d.

The Neutralizing Antibody Assay (IMMUNO-COV REGN2118) is a functional assay that detects the presence of specific neutralizing antibodies capable of inhibiting vesicular stomatitis virus (VSV)- SARS2-Fluc. Infection by VSV-SARS2-Fluc results in the expression of firefly luciferase within Vero cells overexpressing the Ace-2 receptor (Vero-Ace-2). Luciferase substrate (d-luciferin) is added to assay plates to allow for a luminescence readout. The total luminescence (relative light units, RLU) corresponds to the extent of infection by VSV-SARS2-Fluc. The ability of antibodies in human serum to block infection of Vero-Ace-2 cells by VSV-SARS2-Fluc by 50% serves as a proxy readout for antibodies capable of neutralizing SARS-CoV-2 infection.

4.5.2. Secondary Vaccine Response Variables

The secondary vaccine response variables in this study include:

- Absolute values, change from baseline, and percentage change from baseline in concentrations of vaccine-induced antibodies to the following SARS-CoV-2 antigens over time:
 - Anti-S protein
 - Anti-RBD

- Other S protein subdomains (including S1, S2, and NTD)
- 50% inhibitory dilution (ID₅₀) neutralizing antibody titers of vaccine-induced neutralizing antibodies to SARS-CoV-2 S protein assessed over time after the first dose of Moderna mRNA 1273 vaccine

The time points of the secondary vaccine response variables include 0, 6, 14, 28, 42, 56 days after the first dose of Moderna mRNA 1273 vaccine, except that day 56 is not applicable to the variable of 50% inhibitory dilution (ID₅₀) titers of vaccine-induced neutralizing antibodies to SARS-CoV-2. In addition, variables associated with 6 days after the first dose of Moderna mRNA 1273 vaccine are only applicable to study arms 6d and 9, which corresponds to study day 7 for these two arms. Variables will be reported in both BAU/mL and AU/mL units.

4.5.3. Exploratory Vaccine Response Variables

The exploratory vaccine response variables in this study include

- Absolute percentages, change, and percentage change from baseline of blood-derived memory T cell responses specific to SARS-CoV-2 viral peptides over time
- Absolute percentages, change, and percentage change from baseline of blood-derived B cell responses specific to SARS-CoV-2 S protein, RBD, and other S protein subdomains over time

The time points of the exploratory vaccine response variables include 0, 6, 14, 28, 42, 56 days after the first dose of Moderna mRNA 1273 vaccine. In addition, variables associated with 6 days after the first dose of Moderna mRNA 1273 vaccine are only applicable to study arms 6d and 9, which corresponds to study day 7 for these two arms.

4.5.4. Additional Vaccine Response Variables

World Health Organization (WHO) standard units (IU/mL) as well as Viral Neutralizing Titer (VNT) are collected and will be reported.

4.6. Safety Variables

4.6.1. Adverse Events and Serious Adverse Events

Adverse events and serious adverse events will be collected from the time of informed consent signature and then at each visit until the end of the study. All adverse events are to be coded to a PT and associated SOC according to the latest version of MedDRA®.

For safety variables, the following observation periods are defined:

- The **pre-vaccination period** is defined as the time from study drug administration to the first vaccine dose administration.
- The **primary series vaccination period** is defined as the time from the first vaccine dose administration to 28 days after the second vaccine dose administration, and in subjects receiving only one dose of the vaccine, 28 days after the first vaccine dose administration.

- The **post primary series vaccination period** is defined as the time from the end of the primary series vaccination period to the end of the follow-up period in subjects who do not receive the sub-study provided vaccine booster. In subjects who receive the sub-study provided vaccine booster dose, the post-primary series vaccination period is defined as the time from the end of the primary series vaccination period to the administration of the sub-study provided vaccine booster.
- The **post-booster vaccination period** is defined as the time from the sub-study provided vaccine booster to the end of the follow-up period.

Treatment-emergent adverse events are defined as those that are not present at the time of the first dose of Moderna mRNA-1273 Vaccine or REGN10933+REGN10987 (as applicable and whichever occurs first) or represent the exacerbation of a pre-existing condition.

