In addition to the above use case scenarios, the study will evaluate endogenous immune responses over time when 1200 mg IV of REGN10933+REGN10987 is administered 6 days after the first dose of Moderna mRNA-1273 (ie, study day 7). This interval was chosen to allow adequate

production and presentation of S protein antigens following vaccination and is thus intended to represent a scenario in which the immune system is “primed” prior to treatment with REGN10933+REGN10987. This will allow for assessment of safety of REGN10933+REGN10987 administration in close temporal proximity to vaccination. In the event REGN10933+REGN10987 is found to interfere with the endogenous immune response to vaccination when given prior to or concomitantly with vaccination, this will allow assessment of whether, in the prophylaxis setting, vaccination prior to REGN10933+REGN10987 administration will allow high risk subjects to receive both long term and short term protection from vaccination and REGN10933+REGN10987 administration followed shortly thereafter.

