2. INVESTIGATION PLAN

2.1. Study Design and Randomization

This study is a phase 2, randomized, open-label, parallel group study in healthy adult volunteers to assess the immunogenicity, safety, and tolerability of Moderna mRNA-1273 vaccine when administered with REGN10933+REGN10987.

At screening, eligible subjects were to be assigned to an enrollment wave. The enrollment waves were intended to avoid or minimize the potential for unused doses of Moderna mRNA-1273 COVID-19 vaccine (Protocol Section 3.2.1 for additional rationale). Every effort was made by sites to avoid unused doses of vaccine.

Every effort was made by the site to ensure balance of age (<65 years and \geq 65 years) within each of the enrollment waves. At baseline (day 1), subjects were to be randomized to the corresponding study arms in each wave as described in [Table 1](#).

Randomization was performed according to a computer-generated randomization scheme provided by an interactive web response system (IWRS) to a designated study pharmacist or a qualified designee.

Randomization was stratified by age (<65 years versus \geq 65 years).

Table 1: Study Treatment Assignment

Study Arm	Randomization Ratio	Targeted Enrollment	Co-administered REGN10933+REGN10987 Combination Therapy	Moderna mRNA-1273 Vaccine*
Enrollment Wave 1				
1	2	30	1200 mg (600 mg of each mAb) IV on day 1	On day 15 and day 43
2	2	30	300 mg (150 mg of each mAb) IV on day 1	On day 15 and day 43
3	2	30	150 mg (75 mg of each mAb) IV on day 1	On day 15 and day 43
6a	1	15	None	On day 15 and day 43
Enrollment Wave 2				
4	2	30	1200 mg (600 mg of each mAb) SC on day 1	On day 1 and day 29
5	2	30	600 mg (300 mg of each mAb) SC on day 1	On day 1 and day 29
6b	1	15	None	On day 1 and day 29
Enrollment Wave 3				
7	15	30	48 mg (24 mg of each mAb) IV on day 1	On day 15 and day 43
8	15	30	12 mg (6 mg of each mAb) IV on day 1	On day 15 and day 43
6c	4	8	None	On day 15 and day 43
Enrollment Wave 4				
9	15	30	1200 mg (600 mg of each mAb) IV on day 7	On day 1 and day 29

6d	4	8	None	On day 1 and day 29
----	---	---	------	---------------------

*Moderna mRNA-1273 vaccine will be administered as described on the US FDA EUA HCP Fact Sheet, 2021)
mAb=monoclonal antibody; SC=subcutaneous; IV=intravenous.

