4.6.2. Adverse Events of Special Interest

AESIs are AEs (serious or non-serious) required to be monitored, documented, and managed in a pre-specified manner as described in the protocol. In this study, AESI are listed below (as provided in the protocol):

- Grade ≥ 2 infusion-related reactions to REGN10933+REGN10987 through day 4
- Grade ≥ 3 injection-site reactions to REGN10933+REGN10987 or each dose of Moderna mRNA-1273 vaccine through day 4 post-injection
- Grade ≥ 2 hypersensitivity reactions to REGN10933+REGN10987 or each dose of Moderna mRNA-1273 vaccine through day 29 post-infusion or post-injection (as applicable)

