5.8.1. Adverse Events

All AEs reported in this study will be coded using the currently available version of MedDRA®. Coding will be to lowest level terms. The PT and the primary SOC will be listed.

All adverse events will be provided in a listing. Listing of deaths and other SAEs will also be provided.

Tabulations by treatment group will include the following:

All periods combined

- Overview of TEAEs
- TEAEs by SOC and PT
- TEAEs by SOC and PT and Severity
- Serious TEAEs by SOC and PT
- Study Drug Related TEAEs by SOC and PT
- Vaccine Related TEAEs by SOC and PT
- Study Drug Related Infusion Related Reaction TEAEs by SOC and PT

- Study Drug Related Injection Site Reaction TEAEs by SOC and PT
- Vaccine Related Injection Site Reaction TEAEs by SOC and PT
- Study Drug Related Hypersensitivity Reaction TEAEs by SOC and PT
- Vaccine Related Hypersensitivity Reaction TEAEs by SOC and PT
- Treatment-Emergent AESIs by SOC and PT
- TEAEs leading to permanent discontinuation of vaccine by SOC and PT
- TEAEs leading to permanent discontinuation of study drug by SOC and PT
- TEAEs leading to death by SOC and PT

Pre-vaccination period

- Overview of TEAEs
- TEAEs by SOC and PT
- TEAEs by SOC and PT and Severity
- Serious TEAEs by SOC and PT
- Study Drug Related TEAEs by SOC and PT
- Study Drug Related Infusion Related Reaction TEAEs by SOC and PT
- Study Drug Related Injection Site Reaction TEAEs by SOC and PT
- Study Drug Related Hypersensitivity Reaction TEAEs by SOC and PT
- TEAEs leading to permanent discontinuation of study drug by SOC and PT
- TEAEs leading to death by SOC and PT

Primary series vaccination period and Post-booster vaccination period

- Overview of TEAEs
- TEAEs by SOC and PT
- TEAEs by SOC and PT and Severity
- Serious TEAEs by SOC and PT
- Study Drug Related TEAEs by SOC and PT
- Vaccine Related TEAEs by SOC and PT
- Study Drug Related Infusion Related Reaction TEAEs by SOC and PT
- Study Drug Related Injection Site Reaction TEAEs by SOC and PT
- Vaccine Related Injection Site Reaction TEAEs by SOC and PT
- Study Drug Related Hypersensitivity Reaction TEAEs by SOC and PT
- Vaccine Related Hypersensitivity Reaction TEAEs by SOC and PT

- TEAEs leading to permanent discontinuation of vaccine by SOC and PT
- TEAEs leading to permanent discontinuation of study drug by SOC and PT
- TEAEs leading to death by SOC and PT

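### Arm 9's safety periods have no cut at the day 7 infusion, so its all-cause and vaccine-related TEAE tables include six pre-drug days and understate a post-infusion difference

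*SAP*

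**What the plan says.** SAP Table 1 (Section 2.1) gives arm 9 "1200 mg (600 mg of each mAb) IV on day 7" and vaccine "On day 1 and day 29". Protocol 3.2.1.1 describes the same sequence: the antibody "is administered 6 days after the first dose of Moderna mRNA-1273 (ie, study day 7"). It gives a safety reason for the arm: "This will allow for assessment of safety of REGN10933+REGN10987 administration in close temporal proximity to vaccination".

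SAP 4.6.1 defines four safety periods. The first, called the pre-vaccination period in the SAP, "is defined as the time from study drug administration to the first vaccine dose administration". Next comes a primary series vaccination period, which "is defined as the time from the first vaccine dose administration to 28 days after the second vaccine dose administration". The other two cover the time up to and after a sub-study booster. Protocol 11.4.6.1 defines the periods in the same way. None of them starts or ends at an infusion given after the first vaccine dose. The partial-date rules in SAP 6.3 do name arm 9, but place it with the vaccine-only arms 6a to 6d.

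TEAEs are counted from the first dose of vaccine or drug, whichever comes first. Under the as-treated rule in SAP Section 3, anyone who receives drug belongs to a combination arm, and anyone who receives vaccine only moves to the vaccine-alone arm of the same wave. SAP 5.8.1 tabulates TEAEs by treatment group for all periods combined, for the pre-vaccination period, and under the heading "Primary series vaccination period and Post-booster vaccination period". No listed table starts at the arm 9 infusion.

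**The concern.** In the arms that receive drug first, the SAP separates the time on drug alone from the time after vaccination. Arm 9 has the reverse order, and no reverse split is made. Between day 1 and the infusion, arm 9 and its concurrent control 6d have had the same treatment, yet arm 9's events in those days are tabulated as vaccine plus study drug.

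A subject already counted for a reaction to dose 1 cannot be counted again when the same kind of event follows the infusion. A real difference after the infusion is pulled toward zero in the tables a reader would use to judge the arm's stated safety purpose. The vaccine-related tables share the problem because they are not split by dose: dose 1 precedes the drug and dose 2 follows it.

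**Working it through.** **Timing.** Inputs are the study days in SAP Table 1. Day 7 − day 1 = 6 days, which reproduces the interval stated in Protocol 3.2.1.1. Arm 9's primary series period is 28 days (day 1 to day 29) plus 28 days, so 56 days, ending on day 57. The pre-drug share is 6/56 = 10.7%. With the dose 2 visit window of −1 to +3 days, the period is 55 to 59 days and the share 10.9% to 10.2%. Arm 9's pre-vaccination period would have to run from day 7 back to day 1, so it is empty.

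**Dilution.** Protocol 11.4.6.1 counts subjects with at least one event. Let p1 be the probability of the event between dose 1 and infusion, equal in expectation in arms 9 and 6d because they are randomized and treated alike until then. Let q1 and q0 be the post-infusion probabilities with and without drug. If early and late events are independent:

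- proportion with any event = 1 − (1 − p1)(1 − q)
- tabulated difference = (1 − p1)(q1 − q0)

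Without independence, the same formula holds with q1 and q0 taken among subjects who had no pre-drug event. What is lost is p1 times the drug effect among subjects already counted.

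**Illustration.** The documents give neither p1 nor event rates, so all values here are assumptions. With q1 = 70% and q0 = 50%:

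| p1 | Vaccine alone | Vaccine + drug | Difference |
|---|---|---|---|
| 0 | 50% | 70% | 20 points |
| 10% | 55% | 73% | 18 points |
| 30% | 65% | 79% | 14 points |
| 50% | 75% | 85% | 10 points |

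With q1 = 50% and q0 = 20%, a 30-point difference reads as 27, 21 and 15 points at p1 = 10%, 30% and 50%, and the risk ratio of 2.50 as 1.96, 1.48 and 1.25.

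**Which tables.** Here p1 refers to the event being tabulated. For any TEAE it is the share with any pre-drug event. For a single preferred term it is the share with that term, and for serious TEAEs the share with a serious pre-drug event, which should be small.

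**Uninfused subjects.** An arm 9 subject vaccinated but never infused moves to 6d under the as-treated rule. With 8 planned in 6d, one such subject makes 9 and carries 1/9 = 11% of that group's proportion. If the infusion was withheld because of a dose 1 reaction, that reaction enters the control group.

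**The case against.** A reader might infer that every safety output for arm 9 is diluted. The documents do not support that. SAP 5.8.1 tabulates drug-related TEAEs, infusion reactions and drug hypersensitivity separately from vaccine-related events. Protocol 10.2.5 has causality judged separately for drug and vaccine, with timing as a factor, and SAP 6.3 imputes a missing drug relationship as related only when onset follows the drug. The infusion-reaction endpoint is timed from the infusion. A pre-drug event should not enter these outputs.

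A reader might also take the injection-site AESI window after "each dose of Moderna mRNA-1273 vaccine through day 4 post-injection" as a defect, because after dose 1 it closes before arm 9 has had any drug. It is not: it simply describes a vaccine-only interval, arm 9's drug is intravenous, and the dose 2 window follows the infusion.

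Nor is a test weakened, since Protocol 11.1 plans none. High values of p1 have no support in the documents: Protocol 10.1.1 has subjects questioned in general terms about adverse events. Finally, counting from day 1 is a fair description of the whole regimen against vaccine alone, and the SAP follows the protocol's period definitions.

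All of this stands, and it limits the point without removing it. The drug-related tables do not show whether drug given between doses worsens reactions to dose 2, because such reactions could well be attributed to the vaccine. Causality is judged open-label, so the all-cause comparison is the check on that judgment, and it is one of the diluted comparisons. The all-AE listing would let a reader rebuild the split, but the SAP's own aim is to pre-specify its analyses.

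**Conclusion.** The point holds for the all-cause TEAE tables (overview, SOC and PT, severity, serious) and the vaccine-related tables for arm 9. The timing and the missing cut follow directly from the documents. The size does not: it is a factor of about (1 − p1), and p1 is unknown. It ranges from slight for serious or non-overlapping terms to a halving of the any-TEAE difference if half the subjects report something in the first six days. The figures assume equal p1 in both groups and, for the factor to apply to the overall post-infusion difference, independence of early and late events.

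The effect is attenuation, not a false signal of harm, and it concerns a descriptive table rather than an error rate. The change is worth making because it is cheap and serves a purpose the protocol states for this arm. It supplements the whole-regimen tables; it does not show them to be wrong.

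**What to change.** Keep the planned tables. Then:

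- In SAP 4.6.1, define for arm 9 a sub-period from infusion to 28 days after dose 2, and a separate pre-drug sub-period from dose 1 to infusion. Record this in SAP 1.2.5, since Protocol 11.4.6.1 has no such cut.
- In SAP 5.8.1, add all-cause and vaccine-related TEAE tables for the post-infusion sub-period. The main comparator is concurrent control 6d from its day 7 visit (or 6 days after dose 1), among subjects still in the study at that point. The pooled vaccine-alone group, from 6 days after dose 1, is secondary; arms 6a to 6c have no scheduled visit at that point. Show the pre-drug sub-period separately.
- List any arm 9 subject who was vaccinated but not infused, so that their events do not appear only within 6d.
- Extend the partial-date rule in SAP 6.3 to the new cut.

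No new data are needed: onset dates are collected, and arms 9 and 6d share the day 7 visit. The cost is a few sentences in the SAP and one extra table set. The concurrent comparison will remain imprecise, with 30 planned in arm 9 against 8 in 6d.
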